5. STUDY DESIGN

5.1. Overall Design

[figure not shown]
A study design schematic is depicted in [Figure 1](#).

- Study 206889 is a Phase IIa single center, open-label study evaluating the PK of repeat oral doses of gepotidacin in adult female participants with clinical signs and symptoms of acute cystitis.
- All participants who meet the study entry criteria and provide informed consent will receive oral gepotidacin 1500 mg BID for 5 days (total of 10 doses).
- Pretreatment and posttreatment PK collections will be performed throughout the study. Appropriate safety, efficacy, microbiological, and exploratory assessments will also be conducted throughout the study.
- The study duration is approximately 28 days comprising approximately 5 days of confinement at the clinic followed by 2 outpatient visits as follows (see [Table 1](#) and [Section 9](#) for study visit details):
 - Clinic Confinement Visits
 - Baseline (Day -1 to Day 1 predose) Visit
 - On-Therapy (Day 1 to Day 5) Visit
 - Outpatient Visits
 - Test-of-Cure (TOC) (Day 10 to 13) Visit
 - Follow-up (Day 28) Visit
- Participants will be confined to the clinic from Baseline through the On-Therapy Visit. Participants will return to the clinic for the TOC and Follow-up Visits.

Note: At the discretion of the investigator, for emergency purposes only, participants may temporarily leave the clinic on study days without serial PK collections and only

at times that do not interfere with required study assessments. Participants will be instructed to follow the protocol restrictions. The investigator will ensure the participant is eligible to continue in the study upon return to the clinic. All doses of study treatment will be administered under site staff supervision in the clinic.

- Participants with a concomitant fungal infection can only be treated with topical antifungals per local standard of care.
- At any time during the study, participants experiencing new or continuing signs and symptoms of acute cystitis will be assessed and treated per the investigator's judgement. If a participant is switched to a different antibiotic before or during the TOC Visit, all TOC procedures should be completed before the other antibiotic is started. Any participant who discontinues from the PK portion of the study should return for the TOC and Follow up-Visits.

Figure 1 Study Design Schematic

BID=twice daily; PK=pharmacokinetic; TOC=test of cure; WBC=white blood cell.

- Serial blood PK sampling will be performed for the first dose of study treatment on Day 1 and for the time-matched dose on Day 4. Blood samples will be collected predose and at 0.5, 1, 1.5, 2, 3, 4, 6, 8, and 12 hours postdose.
- Serial urine PK sampling will be performed for the first dose of study treatment on Day 1 and for the time-matched dose on Day 4. Urine samples will be collected predose and at intervals of 0 to 2 hours, 2 to 4 hours, 4 to 6 hours, 6 to 8 hours, 8 to 10 hours, and 10 to 12 hours postdose.
- Predose PK blood samples will be collected before each time-matched dose on Days 1 through 5. Predose PK urine samples will be collected 0 to 2 hours before each time-matched dose on Days 1 through 5. Only 1 sample is needed when serial and predose samples overlap.
- Participants will check-out of the clinic after all study procedures have been performed, including a predose clean-catch midstream urine sample for Gram stain, quantitative bacteriology culture, and antimicrobial susceptibility testing, predose PK sample collections, and safety assessments. Participants should remain in the clinic to complete a total of 10 doses. Participants will be instructed to return for the TOC (Day 10 to 13) and Follow-up (Day 28±3) Visits.

5.2. Number of Participants

Approximately 25 to 30 participants will be enrolled to achieve approximately 20 participants who complete the study assessments through Day 5 and are evaluable for the PK analyses.

If participants prematurely discontinue the study, additional replacement participants may be recruited at the discretion of the sponsor and in consultation with the investigator.

5.3. Participant and Study Completion

A participant is considered to have completed study treatment if she has taken all doses of the study treatment and completed the TOC Visit. A participant is considered to have completed the study if she has completed all study visits including the Follow-up Visit.

The end of the study is defined as the date of the last visit of the last participant in the study.

5.4. Scientific Rationale for Study Design

This Phase IIa study is designed primarily to evaluate plasma and urine pharmacokinetics of gepotidacin in participants with acute cystitis. Serial sample collections will be performed on Day 1 (first dose) and on Day 4.

As this PK study will be conducted in female participants with acute cystitis, the exploratory clinical and microbiological efficacy of gepotidacin will also be assessed. The time points and success definitions were based on the Food and Drug Administration (FDA) guidance for industry for developing drug treatments for uncomplicated and complicated UTIs [DHHS, 1998; DHHS, 2015] and the European Medicines Agency (EMA) addendum to the guideline on the evaluation of medicinal products indicated for treatment of bacterial infections [EMA, 2013].

Efficacy will be assessed daily during the On-Therapy Visit, at TOC, and at Follow-up. Clinical success is defined as the resolution of signs and symptoms of acute cystitis present at Baseline (and no new signs and symptoms) and no use of other antimicrobial therapy. Microbiological success is defined as the reduction of the qualifying bacterial uropathogen (defined in [Appendix 9](#)) recovered at Baseline to $<10^3$ colony-forming units (CFU)/mL as observed on quantitative urine culture. Therapeutic success refers to participants who have been deemed both a microbiological success and a clinical success (i.e., responders).

Adult (≥ 18 to ≤ 65 years of age) eligible female participants will be enrolled in this open-label Phase IIa PK study. This age range was selected to minimize variability in systemic exposures as well as baseline uropathogens. This study in acute cystitis is restricted to female participants per the FDA guidance [DHHS, 1998]. As described in [Section 5.5](#), the dose of gepotidacin and the 5-day duration were selected to provide efficacious treatment for acute cystitis and is in alignment with current clinical practice.

5.5. Dose Justification

The oral gepotidacin dose in this study is 1500 mg BID (total daily dose of 3000 mg) for 5 days. A 5-day dosing duration is in alignment with current treatment guidelines for efficacious antibacterial treatment of uncomplicated acute cystitis in women, which typically ranges from 3 to 7 days [Gupta, 2011b; GOV.UK, 2017; EAU, 2017]. The safety and tolerability at this oral dose and duration have been evaluated in Phase I studies and in a Phase II study (BTZ116704) (see Section 5 of the IB for details). Furthermore, high urine concentrations of gepotidacin are expected in this study based on a Phase I study (BTZ117351) where approximately 285 mg of unchanged gepotidacin was excreted in urine after a single, oral, 1500-mg (2×750 -mg tablets) dose of gepotidacin.

The gepotidacin dose and duration for this Phase IIa PK uncomplicated UTI study were selected based on in vitro and in vivo studies including experimental animal pyelonephritis studies that simulated human PK exposures of gepotidacin to determine the efficacy of gepotidacin against isolates of *E. coli*, including MDR strains (see Section 4.2 of the IB for further details).

Additionally, preliminary data from a recently completed in vitro study to determine the PK/PD characteristics of gepotidacin against *E. coli* (dose-fractionation and dose-ranging studies) indicate that AUC/minimum inhibitory concentration (MIC) is the primary PK/PD index predictive of gepotidacin efficacy against *E. coli*. The magnitude of the ratio of the area under the free-drug concentration-time curve to MIC over 24 hours (*fAUC*/MIC) required to achieve net bacterial stasis as well as 1- and 2-log reductions in bacterial burden from baseline across multiple *E. coli* isolates with gepotidacin MIC values ranging from 1 to 4 $\mu\text{g/mL}$, were 34.5, 41.3, and 49.7, respectively.

A set of duplicate 10-day hollow fiber infection model studies were also completed using *E. coli* isolate NCTC 13441 to determine the *fAUC*/MIC exposure of gepotidacin required to prevent the amplification of resistant subpopulation. An inverted-U shaped function described the relationship between drug resistance amplification and *fAUC*, with *fAUC* values ≥ 549 preventing resistance amplification to gepotidacin for *E. coli* in the hollow fiber infection model. This equates to an *fAUC*/MIC value ≥ 275 when applying the gepotidacin broth microdilution MIC of 2 $\mu\text{g/mL}$ for *E. coli* 13441, as determined in this study.

When taking the *fAUC*/MIC target of 275 for resistance suppression into consideration with the concentrations of gepotidacin in human urine measured in a Phase I study (BTZ117351, minimum *fAUC*_{12h}=807 $\mu\text{g}\cdot\text{h/mL}$, so *fAUC*_{24h}=1610 $\mu\text{g}\cdot\text{h/mL}$) and, applying an MIC value of 4 $\mu\text{g/mL}$, the minimum human urine *fAUC*/MIC achieved for the 1500 mg oral BID dose exceeds the *fAUC*/MIC resistance suppression target of 275 by approximately 1.5-fold and 100% target attainment for an *fAUC*/MIC target of 275 would be expected for participants with *E. coli* isolates with gepotidacin MICs ≤ 4 $\mu\text{g/mL}$ following 1500 mg BID oral dosing.

In conclusion, minimum urine levels of gepotidacin are anticipated to be in excess of the *fAUC*/MIC target necessary for both efficacy and resistance suppression for *E. coli* as

determined from the in vitro PK/PD models. Given that the bladder is the primary site of infection in cystitis, the use of gepotidacin urine PK data, coupled with the robust in vivo efficacy demonstrated in the human simulated PK pyelonephritis model, is appropriate for selecting the gepotidacin 1500 mg BID oral dose for 5 days for study in the treatment of participants with acute cystitis.

6. STUDY POPULATION

Prospective approval of protocol deviations to recruitment and enrollment criteria, also known as protocol waivers or exemptions, is not permitted.

6.1. Inclusion Criteria

Otherwise healthy participants are eligible to be included in the study only if all of the following criteria apply:

Age

1. Participant must be ≥ 18 to ≤ 65 years of age inclusive, at the time of signing the informed consent.

Type of Participant and Disease Characteristics

2. The participant has 2 or more of the following clinical signs and symptoms of acute cystitis with onset ≤ 72 hours of the screening assessment: dysuria, frequency, urgency, or lower abdominal pain (see [Appendix 10](#)).
3. The participant has pyuria (≥ 10 WBC/mm³ or the presence of leukocyte esterase) and/or nitrite from a pretreatment clean-catch midstream urine sample based on local laboratory procedures.

Note: Repeat baseline urine samples are allowed if contamination, defined as ≥ 10 squamous epithelial cells, is observed under microscopic evaluation.

Sex

4. The participant is female. A female participant is eligible to participate if she is not pregnant ([Appendix 6](#)), not breastfeeding, and at least 1 of the following conditions applies:
 - Not a woman of childbearing potential (WOCBP) as defined in [Appendix 6](#)OR
 - A WOCBP who agrees to follow the contraceptive guidance in [Appendix 6](#) from the Baseline Visit through completion of the TOC Visit.

Informed Consent

5. Capable of giving signed informed consent as described in [Appendix 3](#), which includes compliance with the requirements and restrictions listed in the informed consent form (ICF) and in this protocol.

6.2. Exclusion Criteria

Participants are excluded from the study if any of the following criteria apply:

Medical Conditions

1. The participant resides in a nursing home or dependent care-type facility.
2. The participant has a body mass index ≥ 40.0 kg/m² or a body mass index ≥ 35.0 kg/m² with obesity-related health conditions such as high blood pressure or uncontrolled diabetes.
3. The participant has a history of sensitivity to the study treatment, or components thereof, or a history of a drug or other allergy that, in the opinion of the investigator or medical monitor, contraindicates her participation.
4. The participant is immunocompromised or has altered immune defenses that may predispose the participant to a higher risk of treatment failure and/or complications (e.g., renal transplant recipients, participants with clinically significant persistent granulocytopenia [absolute neutrophil count $< 1000/\mu\text{L}$], and participants receiving immunosuppressive therapy, including corticosteroid therapy [> 40 mg/day prednisolone or equivalent for > 1 week or ≥ 20 mg/day prednisolone or equivalent for > 6 weeks; or prednisolone or equivalent ≥ 10 mg/day for > 6 weeks]). Participants with a known CD4 count of < 200 cells/mm³ should not be enrolled. **Note:** Participants with a positive test for human immunodeficiency virus are eligible for study participation.
5. The participant has uncontrolled diabetes, defined as a nonfasting glucose value > 300 mg/dL or based on investigator judgment.
6. The participant has any of the following:
 - A medical condition that requires medication that may be aggravated by inhibition of acetylcholinesterase, such as:
 - Poorly controlled asthma or chronic obstructive pulmonary disease at Baseline and, in the opinion of the investigator, not stable on current therapy
 - Acute severe pain, uncontrolled with conventional medical management
 - Active peptic ulcer disease
 - Parkinson disease
 - Myasthenia gravis
 - A history of seizure disorder requiring medications for control (this does not include a history of childhood febrile seizures)

OR

- Any surgical or medical condition (active or chronic) that may interfere with drug absorption, distribution, metabolism, or excretion of the study drug (e.g., ileostomy or malabsorption syndrome). Participants who have had a gastric bypass or a cholecystectomy are excluded from the study.

OR

- Hemoglobin value <12 g/dL or a known uncorrected iron deficiency.
7. The participant, in the judgment of the investigator, would not be able or willing to comply with the protocol or complete study follow-up.
 8. The participant has a serious underlying disease that could be imminently life threatening, or the participant is unlikely to survive for the duration of the study period.

Urinary Tract Infection/Renal/Urogenital Exclusions

9. The participant has acute cystitis that is known or suspected to be due to fungal, parasitic, or viral pathogens; or known or suspected to be due to *Pseudomonas aeruginosa* or *Enterobacteriaceae* (other than *E. coli*) as the contributing pathogen.
10. The participant has symptoms known or suspected to be caused by another disease process such as asymptomatic bacteriuria or chronic interstitial cystitis.
11. The participant has an anatomical or physiological anomaly that predisposes the participant to UTIs or may be a source of persistent bacterial colonization, including calculi, obstruction or stricture of the urinary tract, primary renal disease (e.g., polycystic renal disease), or neurogenic bladder, or the participant has a history of anatomical or functional abnormalities of the urinary tract (e.g., chronic vesico-ureteral reflux, detrusor insufficiency).
12. The participant has an indwelling catheter, nephrostomy, ureter stent, or other foreign material in the urinary tract.
13. The participant who, in the opinion of the investigator, has an otherwise complicated UTI, an active upper UTI (e.g., pyelonephritis, urosepsis), signs and symptoms onset ≥ 96 hours before the screening assessment, or a temperature $\geq 101^\circ\text{F}$, flank pain, chills, or any other manifestations suggestive of upper UTI.
14. The participant has anuria, oliguria, or significant impairment of renal function (creatinine clearance < 30 mL/min or clinically significant elevated serum creatinine).
15. The participant presents with vaginal discharge at Baseline (e.g., suspected sexually transmitted disease).

Cardiac Exclusions

16. The participant has congenital long QT syndrome or known prolongation of the corrected QT (QTc) interval.
17. The participant has uncompensated heart failure, defined as New York Heart Association Class \geq III.
18. The participant has severe left ventricular hypertrophy.
19. The participant has a family history of QT prolongation or sudden death.
20. The participant has a recent history of vasovagal syncope or episodes of symptomatic bradycardia or bradyarrhythmia within the last 12 months.
21. The participant is taking QT-prolonging drugs or drugs known to increase the risk of torsades de points (TdP) per the www.crediblemeds.org "Known Risk of TdP"

category at the time of her Baseline Visit, which cannot be safely discontinued from the Baseline Visit to the TOC Visit; or the participant is taking a strong cytochrome P450 enzyme 3A4 (CYP3A4) inhibitor or a strong P-glycoprotein (P-gp) inhibitor.

Cardiac ECG Exclusion

22. The participant has a QTc >450 msec or a QTc >480 msec for participants with bundle-branch block. **Note:** The QTc is the QT interval corrected for heart rate according to either Bazett or Fridericia formula, machine, or manual overread.

Hepatic Exclusions

23. The participant has a known alanine transferase (ALT) value >2 × upper limit of normal (ULN).
24. The participant has a known bilirubin value >1.5 × ULN (isolated bilirubin >1.5 × ULN is acceptable if bilirubin is fractionated and direct bilirubin <35%).
25. The participant has a current or chronic history of liver disease, or known hepatic or biliary abnormalities (with the exception of Gilbert's syndrome or asymptomatic gallstones), including symptomatic viral hepatitis or moderate-to-severe liver insufficiency (Child Pugh class B or C). **Note:** Participants with asymptomatic viral hepatitis are eligible for study participation.

Prior Antibiotic/Antifungal Use Exclusion

26. The participant has received treatment with other systemic antimicrobials or systemic antifungals within 1 week before study entry.

Concomitant Medication Use Exclusion

27. The participant must agree not to use the medications or nondrug therapies from the Baseline Visit through the TOC Visit as detailed in Section [7.7.2](#).

Prior/Concurrent Clinical Study Experience

28. The participant has been previously enrolled in this study or has previously been treated with gepotidacin.
29. The participant has participated in a clinical trial and has received an investigational product within 30 days or 5 half-lives, whichever is longer.

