3.3.1. Risk Assessment

Potential Risk of Clinical Significance	Summary of Data/Rationale for Risk	Mitigation Strategy
Gepotidacin (e.g., GSK2140944)		

Cardiovascular Effects
 
Based on nonclinical data, cardiovascular effects were reversible increase in heart rate and blood pressure (dog and monkey); reversible 10 to 21 msec (4% to 9%) increase in QTc (monkey); and at the highest dose, a reversible 2 to 3 msec (6% to 8%) increase in QRS (monkey).
 
Based on a thorough QTc clinical study, gepotidacin may cause mild, reversible heart rate effects and QT prolongation.
	
In a thorough QTc study, infusion of gepotidacin at doses of 1000 and 1800 mg over 2 hours caused a mild increased heart rate effect of approximately 6 to 10 bpm and QT prolongation measured as $\Delta\Delta$QTcF of 12 to 22 msec. The QT prolongation evolved during the infusion and was quickly reversed over 2 hours after the end of the infusion (see Section 5.2.6 and Section 6 of the IB).
 
No changes in QRS or QTc of clinical concern have been seen in the clinic (Phase I studies and Phase II ABSSSI study) (see Section 6 in the IB). Cardiovascular events reported in the Phase II urogenital gonorrhoea study were ECG ST segment elevation and palpitations (1 participant each) in the 1500-mg treatment group and tachycardia (1 participant) in the 3000-mg treatment group.
	
See Section 6.2 for excluded cardiac conditions. Close monitoring of clinical parameters and AEs (Table 1) will be conducted, and treatment monitoring and evaluation criteria (Section 8.1.2) will be utilized to mitigate cardiovascular effects.
 
As a consequence, participants taking QT-prolonging drugs or strong CYP3A4 inhibitors and/or strong P-gp inhibitors will be excluded.

Potential Risk of Clinical Significance	Summary of Data/Rationale for Risk	Mitigation Strategy

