7.7.2. Prohibited Medications and Nondrug Therapies

At the time of enrollment and/or during the study from the Baseline Visit through the TOC Visit, the participant is prohibited from use of the following medications and nondrug therapies:

- An investigational product within 30 days or 5 half-lives, whichever is longer, of the Baseline Visit.
- Treatment with other systemic antimicrobials or systemic antifungals within 1 week before study entry. Treatment with systemic fluconazole or other systemic antifungals per local standard of care is only allowed after all TOC Visit procedures have been completed.

- Immunosuppressive therapy, including corticosteroid therapy (>40 mg/day prednisolone or equivalent for >1 week or ≥20 mg/day prednisolone or equivalent for >6 weeks; or prednisolone or equivalent ≥10 mg/day for >6 weeks).
- QT-prolonging drugs or drugs with known TdP risk, per the www.crediblemeds.org “Known Risk of TdP” category, at the time of their Baseline Visit, which cannot be safely discontinued from the Baseline Visit to the TOC Visit. Details regarding website access are provided in the SRM.

Note: Crediblemeds.org categorizes drugs into 4 categories. The only category for exclusion in this study is the “Known Risk of TdP” category; participants taking drugs that meet criteria of other categories are NOT excluded from participation.

- Strong CYP3A4 inhibitors (a list of strong CYP3A4 inhibitors is provided in the SRM).
- Strong P-gp inhibitors (a list of strong P-gp inhibitors is provided in the SRM).
- St John’s wort is not permitted from 14 days before study entry through the TOC Visit.
- Prescription, nonprescription, or supplements that may impact UTI clinical or microbiological efficacy outcomes including, but not limited to, *Uva ursi*, cranberry tablets, phenazopyridine, nonsteroidal anti-inflammatory drugs including cyclooxygenase 2 inhibitors, uricosuric drugs (such as probenecid and sulfapyrazone).
- Antacids administration is not permitted within 2 hours before or after study treatment administration.

Due to the gepotidacin’s property of acetylcholinesterase inhibition, the concomitant use of succinylcholine or other nondepolarizing paralytic agents is also prohibited. Caution should be used in participants who have a condition requiring medication that may be exacerbated by acetylcholinesterase inhibition or neuromuscular blocking agents.

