8.1.2. QTc Stopping Criteria

A participant who meets the following bulleted criteria based on the average of triplicate ECG readings will be withdrawn from study treatment:

- QTc >500 msec OR uncorrected QT >600 msec
- Change from baseline of QTc >60 msec

For participants with underlying bundle-branch block, follow the discontinuation criteria listed below:

Baseline QTc with Bundle-Branch Block	Discontinuation QTc with Bundle-Branch Block
<450 msec	>500 msec
450 to 480 msec	≥530 msec

- The *same* QT correction formula *must* be used for *each individual participant* to determine eligibility for and discontinuation from the study. This formula may not be changed or substituted once the participant has been enrolled.
 - For example, if a participant is eligible for the protocol based on QTcB, then QTcB must be used for discontinuation of this individual participant as well.
 - Once the QT correction formula has been chosen for a participant's eligibility, the same formula must continue to be used for that participant *for all QTc data being collected for data analysis*. Safety ECGs and other non-protocol specified ECGs are an exception.
- The QTc should be based on averaged QTc values of triplicate ECGs obtained over a brief (e.g., 5- to 10-minute) recording period.

See [Table 1](#) for data to be collected at the time of treatment discontinuation and follow-up and for any further evaluations that need to be completed.

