
Clinic Confinement Visits

- **Baseline (Day -1 to Day 1 predose) Visit:** The Baseline Visit includes a screening window of up to 24 hours from the time of informed consent to the first dose of study treatment. Baseline assessments performed during the screening window do not need to be repeated before study treatment is started unless indicated as a Day 1 predose assessment in [Table 1](#).

Baseline assessments will be performed, including the following (see [Table 1](#)):

- Participants will provide a pretreatment clean-catch midstream urine sample for confirmation of pyuria (≥ 10 WBC/mm³ or the presence of leukocyte esterase) and/or nitrite per local laboratory procedures.

Note: Repeat baseline urine samples are allowed if contamination, defined as ≥ 10 squamous epithelial cells, is observed under microscopic evaluation.

- Site staff will record clinical signs and symptoms of acute cystitis ([Appendix 10](#)), clinical laboratory samples will be collected, vital signs will be measured, and a triplicate 12-lead ECG and complete physical examination will be performed.
- Participants who meet the eligibility criteria in time to support the first dose of study treatment by 2 PM will be admitted to the clinic on Day 1 and On-Therapy procedures will begin. Participants who meet the eligibility criteria past the first dose time limit of 2 PM may be admitted that same day (Day -1) or the next morning (Day 1); dosing will start on the morning of Day 1.

Day 1 predose assessments will be performed (see [Table 1](#) and [Table 2](#)), including the following:

- An ECG will be performed and vital signs will be measured if the baseline assessment was not within 4 hours of the first dose of study treatment.
 - Participants will provide a pretreatment clean-catch midstream urine sample for Gram stain, quantitative bacteriology culture, and antimicrobial susceptibility testing.
 - Predose blood and urine PK samples will be collected.
 - A stool microbiome specimen will be obtained from participants who consent to provide such specimens.
 - Vaginal and pharyngeal swab microbiome specimens will be obtained from participants who consent to provide such specimens.

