- **On-Therapy (Day 1 to Day 5) Visit:** Participants will be confined to the clinic during the 5-day On-Therapy Visit period, and will receive oral gepotidacin 1500 mg BID for 5 days (total of 10 doses) starting with the first dose on Day 1. All doses of study treatment will be administered under site staff supervision and

all doses will be administered with food (i.e., standardized meals or snacks as applicable).

- The first dose of gepotidacin must be administered by 2 PM on Day 1 and subsequent doses will be administered approximately every 12 hours.
- Only if medically appropriate per the investigator's judgement, for participants who are enrolled after 2 PM, the first dose of study treatment will be postponed until the next morning; nonexclusionary pain medication will be allowed for these participants before study treatment is started.
- Study assessments and PK collections on Days 1 through 5 will be performed relative to the time-matched dose as determined by the first dose of study treatment (e.g., if the first dose is at 11 AM on Day 1 for a participant, then their time-matched dose on subsequent days will be at 11 AM; or, if the first dose is at 1 PM on Day 1 for a participant, then their time-matched dose on subsequent days will be at 1 PM).
- On Day 1, a single 12-lead ECG will be performed at 2 hours after the first dose of study treatment. On Day 4, a single 12-lead ECG will be performed at predose and 2 hours postdose (at the same ECG time points as on Day 1) (see [Table 2](#)).
- Vital sign measurements will be taken daily from Days 2 through 5.
- On Days 2 through 5, before the time-matched dose, clinical signs and symptoms of acute cystitis will be recorded ([Appendix 10](#)) and participants will provide a clean-catch midstream urine sample for Gram stain, quantitative bacteriology culture, and antimicrobial susceptibility testing.
- Blood and urine PK collection (see [Table 1](#), [Table 2](#), and [Section 9.5.1](#)).
- On Day 3, clinical laboratory samples will be collected for hematology, chemistry, and urinalysis.
- On Day 4, at predose and at approximately 2 hours postdose, cervical, rectal, and pharyngeal swab PK specimens will be obtained from participants who consent to provide such specimens.
- On Day 5, a stool microbiome specimen will be obtained from participants who consent to provide such specimens.

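### Exclusion 21 admits a woman who stops a Known Risk of TdP drug at Baseline without a washout, so residual drug can overlap the first gepotidacin doses; Section 3.3.1 describes a broader exclusion

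*Protocol*

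**What the plan says.** Protocol Section 6.2, criterion 21, covers drugs in the Known Risk of TdP "category at the time of her Baseline Visit, which cannot be safely discontinued from the Baseline Visit to the TOC Visit". Section 7.7.2 repeats the condition, and its note limits exclusion to that one category. Neither section gives a washout for these drugs.

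Section 3.3.1, the risk table, lists as mitigation that "participants taking QT-prolonging drugs or strong CYP3A4 inhibitors and/or strong P-gp inhibitors will be excluded". It mentions neither the exception for drugs that can be stopped nor the category limit, though the same cell refers to Section 6.2 for excluded cardiac conditions.

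On timing, Section 9 states: "The Baseline Visit includes a screening window of up to 24 hours from the time of informed consent to the first dose of study treatment". A woman found eligible in time for a 2 PM dose is treated that day.

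The plan sets look-back periods for other agents:
- 1 week for systemic antimicrobials and antifungals (criterion 26)
- 30 days or 5 half-lives, whichever is longer, for investigational products (criterion 29)
- 14 days for one herbal product: St John's "wort is not permitted from 14 days before study entry through the TOC Visit" (Section 7.7.2)

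Section 6.4 bars rescreening for the same infection episode.

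**The concern.** Gepotidacin may itself prolong QT. Section 3.3.1 reports a placebo- and baseline-adjusted QTcF increase of 12 to 22 msec with 2-hour infusions of 1000 and 1800 mg. Excluding users of QT-prolonging drugs is one of the measures offered in response.

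The operative criterion asks whether the other drug can be stopped safely. It does not ask whether that drug will have cleared before gepotidacin starts. Followed exactly, it permits a woman to take her last dose of a Known Risk drug on the morning of screening and her first gepotidacin dose that afternoon. At stake is the safety of the individual woman, and whether the risk table describes the protection that the criteria deliver.

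**Working it through.** The plan states no figure on this point, so there is none to reproduce. The check has three parts.

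**1. Residual drug at the first gepotidacin dose.** Neither the half-life *h* of the stopped drug nor the interval *g* from its last dose to the first gepotidacin dose is in the documents, so both are assumed. With first-order elimination, the fraction remaining is 2^(−g/h).

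| Assumed g | h = 6 h | h = 12 h | h = 24 h | h = 48 h |
|---|---|---|---|---|
| 4 h | 63% | 79% | 89% | 94% |
| 24 h | 6% | 25% | 50% | 71% |
| 48 h | 0.4% | 6% | 25% | 50% |

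Example: g = 24, h = 12 gives 2^(−2) = 25%. After 5 half-lives, 2^(−5) = 3.1% remains. The longest half-life that completes 5 half-lives by the first dose is g/5: 0.8, 4.8 and 9.6 hours for the three intervals.

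**2. Gepotidacin doses given before 5 half-lives have passed.** Section 7.1 gives 10 doses about every 12 hours, at 0, 12, ..., 108 hours. Five half-lives are complete 5h − g hours after the first dose.

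| Assumed g | 5h − g for h = 6, 12, 24, 48 | Doses before that time |
|---|---|---|
| 4 h | 26, 56, 116, 236 h | 3, 5, 10, 10 |
| 24 h | 6, 36, 96, 216 h | 1, 3, 8, 10 |
| 48 h | −18, 12, 72, 192 h | 0, 1, 6, 10 |

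**3. ECG coverage.** This part comes from the documents (Tables 1 and 2, Section 9). An ECG is taken 2 hours after the first dose. The next is at Day 4: "On Day 4, a single 12-lead ECG will be performed at predose and 2 hours postdose". Day 4 predose is 72 hours after the first dose, so 72 − 2 = 70 hours pass with no scheduled ECG. The doses at 12, 24, 36, 48 and 60 hours (doses 2 to 6) fall in that gap.

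**Effect on group summaries.** One such woman among 25 to 30 moves a mean by 1/30 = 3.3% to 1/25 = 4.0% of her own shift. A baseline ECG recorded with residual drug present could also be raised. That would understate her change from baseline, including for the stopping rule "Change from baseline of QTc >60 msec" (Section 8.1.2).

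**The case against.** The case against is substantial, and much of it stands.

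- **The window.** A reader might infer that the 24-hour Baseline window caps the washout, so that only drugs with a half-life of 4.8 hours or less can clear. The documents do not support that. The 24 hours run from consent to first dose, whereas the relevant interval starts at the last dose of the other drug. A woman who last took a once-daily drug 24 hours before consent could have a 48-hour interval.
- **ECGs.** A reader might infer that no ECG sees the two drugs together. The Day 1 2-hour ECG does, soon after the first dose, and residual drug only falls from then on. What remains is the 70-hour gap before the next scheduled ECG.
- **Section 3.3.1.** It is a risk-table summary, and a woman who has stopped a drug is arguably no longer taking it. Sections 6.2 and 7.7.2 agree with each other. This is summary wording broader than the rule, not a conflict between operative criteria.
- **Other look-backs.** None is tied to QT. They show only that the plan sets such intervals elsewhere and already uses a 5-half-life measure. The 1-week rule also covers any Known Risk drug that is a systemic antimicrobial or antifungal.
- **Inhibitors.** The strong CYP3A4 and P-gp inhibitor clause has no washout either. But it excludes every current user, with no exception for a drug that can be stopped.
- **Study Reference Manual.** Section 7.7.2 says "Details regarding website access are provided in the SRM" and also cites the manual for the inhibitor lists. The manual is not available here, so further guidance in it cannot be ruled out.
- **Risk level.** Participants are otherwise healthy and aged 18 to 65. Entry requires QTc of no more than 450 msec (480 msec with bundle-branch block), and cardiac exclusions 16 to 20 apply. Treatment stops at QTc above 500 msec, QT above 600 msec or a change above 60 msec, and women are confined during dosing. Of Phase I and the Phase II skin study, Section 3.3.1 reports: "No changes in QRS or QTc of clinical concern have been seen in the clinic".

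These points reduce the size of the concern. None of them requires the stopped drug to clear before gepotidacin starts.

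**Conclusion.** The point holds at low severity. The criteria as written permit overlap between a Known Risk of TdP drug and the first gepotidacin doses, and Section 3.3.1 describes a broader exclusion than they deliver. The absence of a washout and the 70-hour ECG gap come from the documents. The residual percentages and dose counts rest on assumed half-lives and intervals; they are not converted to msec, and no particular drug is identified.

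The number of women affected is unknown and may be zero. Any effect on group QTc means is small. A reader might infer that the pharmacokinetic results are compromised, but nothing here supports that: the primary PK results are unaffected. The case for change is individual safety and an accurate risk statement.

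**What to change.** - In criterion 21 and Section 7.7.2, replace the condition about safe discontinuation. Exclude anyone who took a Known Risk of TdP drug within 5 half-lives before the first gepotidacin dose, or who needs one before the TOC Visit.
- Record the date and time of the last dose of any such drug at Baseline. Section 7.7 already collects start and end dates, so this adds one question.
- List half-lives for these drugs in the Study Reference Manual, alongside the inhibitor lists it already holds.
- Reword Section 3.3.1 to the same rule, naming the Known Risk category.

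The cost is wording in three sections, one Baseline question and one reference list. Entry becomes slightly narrower: some women who stop such a drug only at Baseline could not join for that episode, because rescreening for it is barred.
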